**Table 4-1 Overall lesion response at each assessment: patients with non-target disease only**

Non-target lesions	New Lesions	Overall lesion response
CR	No	CR
Non-CR/Non-PD 	No	Non-CR/non-PD
UNK	No	UNK
PD	Yes or No	PD
Any	Yes	PD

 In general, the **non-CR/non-PD response** for these patients is considered equivalent to an SD response in endpoint determination.

**Missing baseline tumor assessment**

As specified in Section 14 (Appendix 2) of the protocol, since the timing of PD cannot be determined for patients with missing baseline tumor assessment, these patients are censored in the PFS analysis at the start date of treatment. This rule, however, only applies to the ‘PD component’ of the PFS or DOR assessment.

Patients without baseline tumor assessment who die within D2 distance from start date of treatment will be counted as having an event in the primary analysis of PFS. All deaths will be counted in the OS analysis regardless of presence or absence of the baseline tumor assessment.

**Construction of waterfall graphs**

The waterfall graphs will be used to depict the anti-tumor activity. These plots will display the best percentage change from baseline in the sum of the measured diameter of all target lesions for each patient. The proportions of patients with various degrees of tumor shrinkage or growth can then represent a useful efficacy metric.

However, caution needs to be paid to the assessments, where an occurrence of a new lesion or worsening in non-target lesions (resulting in PD as an overall lesion response at given assessment) contradicts the measurements obtained on target lesions. These assessments will not be displayed as bars in the graph. If such a “contradicting” assessment represents the only post-baseline assessment for a patient, then the patient will be represented by a special symbol (e.g. \*) in the waterfall graph.

The assessments with unknown target response and also assessments with unknown overall response will be excluded. Patients without any valid assessments will be completely excluded from the graphs.

The total number of patients displayed in the graph needs to be shown and this number will be used as a denominator when calculating the percentages of patients with tumor shrinkage and tumor growth. Footnote will explain the reason for excluding some patients (due to absence of any valid assessment).

All possible assessment scenarios are described in [Table 4-2](#).

**Table 4-2 Inclusion/exclusion of assessments used in waterfall graph**

Criteria for inclusion/exclusion			Possible source of contradictions	
Target response	Overall lesion response	Include in waterfall	Non-target response	New lesion?
CR/PR/SD	PD	Yes but as * only	PD	any
CR/PR/SD	PD	Yes but as * only	any	Yes
UNK	UNK or PD	No	any	any
CR/PR/SD	UNK	No	UNK	No
CR/PR/SD	CR/PR/SD	Yes as a bar	SD/IR	No
PD	PD	Yes as a bar	any	any

The following algorithm will be used to construct the graph:

1. Select “valid” post-baseline assessments to be included, i.e. for each patient and each assessment repeat the following four steps:
  - 1.1. Check the target lesion response and overall lesion response at each assessment. If at least one of them is UNK then exclude the whole assessment. Otherwise, go to step 1.2.
  - 1.2. Check the overall lesion response. If PD, then go to step 1.3. Otherwise, go to step 1.4
  - 1.3. Check target response. If PD, then go to step 1.4. Otherwise flag the assessment \*.
  - 1.4. Calculate the % change from baseline in target lesions.
2. For each patient, go through all valid assessments identified in step 1 and find the assessment with best % change from baseline in target lesions. The “best” means best for the patient, i.e. the largest shrinkage or if a patient only has assessments with tumor growth take the assessment where the growth is minimal. (*Example 1*: Patient 1 has the following %

changes from baseline at assessments 1, 2, 3, 4 and 5, respectively: -10%; -25%; -13%; -4% and +6%. His/her best % change is then -25%. *Example 2:* Patient 2 has the following % changes from baseline at assessments 1, 2 and 3, respectively: +5%; +18% and +35%. His/her best % change is then +5%.

3. Construct the waterfall graph displaying the best % change from baseline for each patient. Patients having only ★ flagged assessment(s) will be displayed separately.

The recommended way of the display from left to right is:

1. Bars above the horizontal axis representing tumor growth
2. Bars under the horizontal axis representing tumor shrinkage
3. “Zero” bars with ★ symbol representing patients with contradiction

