4.1.2.2 Central radiology review of locally assessed disease progression

In case patients have equivocal disease progression according to RECIST 1.1 (in the brain, outside of the brain or both) as determined by the investigator, a confirmatory tumor assessment should be done at least 4 weeks thereafter. While the investigator is waiting for the confirmatory tumor assessment, it is preferable that the patient continue on study treatment for as long as it is clinically acceptable. However, during this time, the investigator should do whatever is medically necessary for the patient.

If the investigator does not determine disease progression, the patient should continue receiving the study drug unless there is a medical need (i.e., rapid progression or clinical deterioration) for an immediate change in therapy.

If the investigator confirms disease progression, then the patient will discontinue study drug and subsequent follow-up tumor assessments will no longer be required (except in the cases described below).

Exceptions to the discontinuation of study treatment after progressive disease (PD) being confirmed by the investigator are:

- In case of isolated brain progression with controlled disease outside of the brain, patients may continue the study drug during the treatment of the new brain lesion if appropriate. If

ceritinib has to be interrupted during the treatment of the new brain lesions, it may be resumed after the treatment of the brain lesion if:

- Brain lesions are demonstrated to be controlled by gadolinium-enhanced MRI and if patient is neurologically stable within the last 2 weeks prior to the re-initiation of study drug.
- The disease outside of the brain remains controlled prior to re-initiation of study drug. A new tumor assessment will be repeated if the last one available is older than 4 weeks.
- Time interval between last dose and re-initiation of study drug does not exceed 8 weeks.
- Patient will continue to be followed for safety and efficacy assessments as per schedule of assessment.
- If patient had PD outside of the brain (with minimally symptomatic or no PD in the brain) but still derives clinical benefit from ceritinib following investigator's judgment, patient may continue study drug and continue to be followed for safety and efficacy assessments as per schedule of assessment.

[figure not shown]
[figure not shown]

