Example: In a case where confirmation of response is required the sum of lesion diameters is 200 mm at baseline and then 140 mm - 150 mm - 140 mm - 160 mm - 160 mm at the subsequent visits. Assuming that non-target lesions did not progress, the overall lesion response would be PR - SD - PR - PR - PR. The second assessment with 140 mm confirms the PR for this patient. All subsequent assessments are considered PR even if tumor measurements decrease only by 20% compared to baseline (200 mm to 160 mm) at the following assessments.

If the patient progressed but continues study treatment, further assessments are not considered for the determination of best overall response.

Note: these cases may be described as a separate finding in the CSR but not included in the overall response or disease control rates.

The best overall response for a patient is always calculated, based on the sequence of overall lesion responses. However, the overall lesion response at a given assessment may be provided from different sources:

- Investigator overall lesion response
- Central Blinded Review overall lesion response
- Novartis calculated overall lesion response (based on measurements from either Investigator or Central Review)

The primary analysis of the best overall response will be based on the sequence of investigator/central blinded review/calculated (investigator)/calculated (central) overall lesion responses.

Based on the patients' best overall response during the study, the following rates are then calculated:

Overall response rate (ORR) is the proportion of patients with a best overall response of CR or PR. This is also referred to as 'Objective response rate' in some protocols or publications.

Disease control rate (DCR) is the proportion of patients with a best overall response of CR or PR or SD.

Another approach is to summarize the progression rate at a certain time point after baseline. In this case, the following definition is used:

Early progression rate (EPR) is the proportion of patients with progressive disease within 8 weeks of the start of treatment.

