### 2.7.4 Supportive analyses

Waterfall plots representing the best percentage change from baseline in the sum of the tumor diameters for target lesions will be produced by prior ALKi use (Yes/No) for FAS. See [Section 4.6.1](#) for details on construction of waterfall graphs.

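### SAP 4.6.1: the waterfall algorithm has no cut-off at first progression or at new anticancer therapy, so a bar can overstate, and cannot understate, shrinkage on ceritinib (minor)

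*SAP*

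**What the plan says.** SAP 2.7.4 lists one supportive analysis of the primary endpoint: "Waterfall plots representing the best percentage change from baseline in the sum of the tumor diameters for target lesions", by prior ALK inhibitor use, on the FAS.

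SAP 4.6.1 gives the algorithm. Step 1 selects valid scans: "for each patient and each assessment repeat the following four steps". Step 1.1 handles unknown responses: "If at least one of them is UNK then exclude the whole assessment". Steps 1.2 and 1.3 flag with a star any scan where overall response is PD but target response is not, and the text above Table 4-2 says of these: "These assessments will not be displayed as bars in the graph". Step 2 is then to "go through all valid assessments identified in step 1 and find the assessment with best % change from baseline in target lesions".

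Patients with no valid scan are left out of the graph. The number displayed must be shown, and "this number will be used as a denominator when calculating the percentages of patients with tumor shrinkage and tumor growth". A footnote must explain the exclusions.

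Best overall response (BOR) is handled differently. Under SAP 2.7.1, scans after the start of any further anti-neoplastic therapy do not count. Protocol 14.2.17 adds: "If the patient progressed but continues study treatment, further assessments are not considered for the determination of best overall response".

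**The concern.** The waterfall is meant to depict the same drug effect as the primary endpoint, yet its scan-selection rule omits both stops that protect the primary endpoint. In a study where every patient receives the same drug and the SAP tests no hypothesis, this figure will be read as a picture of ceritinib activity, and SAP 4.6.1 itself describes the resulting proportions as potentially useful for judging efficacy. If a post-progression or post-therapy scan can supply the bar, shrinkage produced by brain radiotherapy, surgery or another drug can be shown as the patient's best result on ceritinib.

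A second, smaller matter is that the plot is announced for the FAS while its percentages are taken over displayed patients only. ORR keeps patients without a post-baseline scan in the denominator as failures.

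**Working it through.** **1. The plan's own examples.** The bar is the minimum, over valid unstarred scans, of 100 × (sum at scan − baseline sum) / baseline sum. Example 1 in SAP 4.6.1 (-10, -25, -13, -4, +6) gives -25%. Example 2 (+5, +18, +35) gives +5%. Both agree with the SAP.

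**2. Example 1 runs past progression.** Let the baseline sum be B. The nadir is 0.75B. The third scan is 0.87B, and 0.87/0.75 = 1.16, so it is not PD. The fourth is 0.96B, and 0.96/0.75 = 1.28, a 28% rise. The absolute rise is 0.21B, which reaches 5 mm when B is at least 5/0.21 = 23.8 mm. For any baseline sum of about 24 mm or more, the fourth scan is therefore target PD under Protocol Table 14-5, yet the fifth is still searched. That patient's bar does not change, but the example shows that no stop is built in.

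**3. The two rules side by side.**

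| Scan or patient | BOR and ORR | Waterfall |
|---|---|---|
| Unknown target or overall response | Does not count as response | Scan excluded |
| Overall PD, target CR/PR/SD | PD | Star, no bar |
| After first PD | Not used (Protocol 14.2.17) | No rule |
| After new anticancer therapy | Not used (SAP 2.7.1) | No rule |
| No valid scan | Non-responder in the FAS | Removed from graph and denominator |

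**4. A constructed patient** (lesion sizes are illustrative). Sums are 100, 90, 75, 95 mm, then 60 mm after brain radiotherapy. The 95 mm scan is 95/75 = +27% and +20 mm over nadir, so target PD.

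- Stopped at PD: the best value is -25%.
- SAP rule, last scan recorded as overall PR: -40%.
- SAP rule, last scan recorded as overall PD with target PR: that scan is starred, and the bar stays at -25%.

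So a later scan changes the bar only if its overall response is recorded as something other than PD and its value beats the earlier best. Since the rule takes a minimum, adding scans can never make an existing bar worse. A patient with only starred scans before the cut-off can also gain a bar from a later scan.

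**5. Whether such scans will exist.** Whole-body target lesions may include brain lesions (Protocol 7.2.1.1). With isolated brain progression, "patients may continue the study drug during the treatment of the new brain lesion if appropriate", and efficacy assessments continue on schedule (Protocol 4.1.2.2). Palliative radiotherapy and surgery are allowed (Protocol 6.4.1.5). Separately, patients who stop ceritinib without progression are scanned every 8 weeks, and new therapy is not among the listed reasons to stop scanning (Protocol 4.1.2.1 and 7.1.6.2, SAP 1.1). SAP Table 2-2, row F, presupposes scans after new therapy. Protocol 7.1.6.3, however, moves patients who start new therapy to survival follow-up, so practice may vary.

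**6. The denominator.** If a share u of the FAS has no valid scan, each percentage is multiplied by 1/(1 − u). The share is not given for this trial. Unknown best response in the earlier 750 mg study was 10.8% (naive), 14.2% (all) and 16.0% (prior ALK inhibitor) in Protocol Table 1-2. I use these as upper-end assumptions, with 5% as an assumed low value. With the planned N = 140 in Arms 1-4 and assumed counts of 84 or 105 patients with shrinkage:

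| Assumed u | Displayed | 84 (60.0% of FAS) | 105 (75.0% of FAS) |
|---|---|---|---|
| 5% | 133 | 63.2% | 78.9% |
| 10.8% | 125 | 67.2% | 84.0% |
| 14.2% | 120 | 70.0% | 87.5% |
| 16.0% | 118 | 71.2% | 89.0% |

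Growth is inflated in the same way: 14 patients are 10.0% of 140, 10.5% of 133 and 11.9% of 118.

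**The case against.** The algorithm is not blind to progression. Starring removes many post-progression scans. The continuation clause quoted above concerns a new brain lesion; a new lesion is always PD (Protocol 14.2.14), so while it remains recorded, later scans become bars only if the target response is itself PD. Follow-up imaging is not required after confirmed PD outside the listed exceptions, and patients progressing both inside and outside the brain continue for safety assessments only. At most two target lesions per organ are chosen, and only about 70 of the 140 patients in Arms 1-4 are expected to have measurable brain disease. All of this stands and limits how often a bar could be affected. It does not cover target-lesion progression in the brain, nor a subsequent drug started without progression.

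Other SAP text could be said to close the gap. SAP 2.7.3 counts patients treated past progression as PD for ORR and other efficacy endpoints, and SAP 4.6.1 treats brain radiotherapy as anticancer therapy for whole-body endpoints. The first assigns a response category; the second sits in the ORR paragraph. Neither says which scan supplies a percentage change.

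On the denominator, the displayed number and a footnote disclose the exclusions, and a patient without a measurement cannot have a bar. That stands; what remains is the mismatch with the FAS named in SAP 2.7.4.

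A reader might infer that every post-baseline scan is searched, that any irradiated brain target is plotted at its post-radiotherapy size, or that the figure contradicts the ORR. The documents support none of these: unknown and starred scans are kept out, the effect needs the two conditions in step 4 of the working, and best target-lesion change and confirmed overall response are different quantities.

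**Conclusion.** The gap is real and minor. The written rule sets no cut-off at first progression or new anticancer therapy, so a later scan recorded as CR, PR or SD can supply the bar. The direction is certain: for a patient who has a bar either way, the plotted change can only be equal or more favourable. The size is not: -25% against -40% is a constructed case, and the documents give no basis for how many bars would move. To say that the plot does overstate activity would go further than they allow.

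The denominator effect is exact as a factor, 1/(1 − u), but u is assumed. The 10.8% to 16.0% values come from another study under RECIST 1.0 and are probably high, because in this SAP an unknown best response includes stable disease too early and progression too late, and such patients may still have a bar. The effect raises growth as well as shrinkage, so it is not a one-sided overstatement of activity.

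ORR, DCR and their confidence intervals do not change. This reading assumes that the waterfall uses whole-body investigator data, which its place under the primary variable implies but SAP 2.7.4 does not state.

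**What to change.** Add a step 0 to the algorithm in SAP 4.6.1: keep only assessments up to and including the first whole-body PD by investigator and before the first new anticancer therapy. Use the region-specific definition already in SAP 4.6.1, under which brain radiotherapy counts for whole-body endpoints, and include surgery to a target lesion. Name the data source: SAP 2.7.1 finds further therapy on the form for treatments after the last dose, which may not hold brain radiotherapy given while ceritinib continues.

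Report the numbers with shrinkage and growth over the FAS number in each prior-ALK-inhibitor group, beside the displayed-patient percentages, with starred and unassessed patients as separate categories so that the counts add up to the FAS.

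The cost is a few lines of programming and a revised footnote. Some bars may become shorter, and the FAS-based percentages will be lower wherever patients are unassessed. No clinical rule, sample size or other endpoint is touched.

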#### 4.6.2 Implementation of RANO guidelines (protocol Appendix 3)

As described in the protocol, intracranial endpoints (OIRR, IDCR, DOIR, and TTIR in the brain) will also be evaluated by RANO criteria as exploratory endpoints. This section provides some details on how to derive these intracranial endpoints by RANO and further details are included in the protocol Appendix 3.

##### RANO vs. RECIST 1.1

In this study, intracranial endpoints will be evaluated by both RECIST 1.1 and RANO. Measurable disease by RANO is defined as bi-dimensionally, contrast-enhancing, measurable lesions with clearly defined margins by CT or MRI scan, with a minimal diameter of 10mm, and visible on 2 axial slices which are at least 5 mm apart with 0 mm skip. Measurement of tumor around a cyst or surgical cavity, if necessary, requires a minimum thickness of 3 mm.

The major differences between RECIST 1.1 and RANO include:

- The measurability criteria for target lesion by RANO is based on two dimensions and is more stringent than the RECIST 1.1 criteria, therefore, the number of target lesions by RANO is no more than the number of target lesions by RECIST 1.1;
- In RECIST 1.1, only one diameter is recorded for each target lesion, while in RANO, two perpendicular diameters are measured for each target lesion;
- In RANO, corticosteroids use and clinical status are also considered for determining overall response;
- There are two types of non-target lesions by RANO: non-enhancing lesions and non-measurable enhancing lesions. Both types of non-target lesions contribute to the non-target lesion response.

##### Overall Lesion Response Collected on RANO eCRF page

Intracranial endpoints by RANO will be derived based on the collected overall lesion response on eCRF page “RANO Overall Lesion Response” (ZR domain, ZRCAT = “RESPONSE ASSESSMENT IN NEURO-ONCOLOGY”, and ZRSCAT = “OVERALL LESION RESPONSE”). The derivation of intracranial endpoints (OIRR, IDCR, DOIR, TTIR and TTP in the brain) by RANO is the same as by RECIST 1.1.

## Calculation of Overall Lesion Response by RANO

Overall lesion responses by RANO are also calculated from the following components:

1. Target lesion measurements;
2. Non-target lesion response;
3. New lesion present (Yes/No);
4. Corticosteroids use;
5. Clinical status.

All these components are collected on the following eCRF pages:

1. RANO target lesion - Measurable enhancing lesion (T1) (ZI domain, ZICAT = "MODIFIED RANO CRITERIA FOR BRAIN METASTASES", ZISCAT = "TARGET ENHANCING T1");
2. RANO non-target lesion - Non-measurable enhancing lesion (T1) (ZI domain, ZICAT = "MODIFIED RANO CRITERIA FOR BRAIN METASTASES", ZISCAT = "NON-TARGET ENHANCING T1");
3. RANO non-target lesion - Non-enhancing lesion (T2/FLAIR) (ZI domain, ZICAT = "MODIFIED RANO CRITERIA FOR BRAIN METASTASES", ZISCAT = "NON-TARGET NON ENHANCING T2/FLAIR");
4. RANO New Lesion (ZI domain, ZICAT = "MODIFIED RANO CRITERIA FOR BRAIN METASTASES", ZISCAT = "NEW");
5. Corticosteroids use and clinical status are collected on the Modified RANO Assessment (ZR domain, ZRCAT = "MODIFIED RANO CRITERIA FOR BRAIN METASTASES", ZISCAT = "RESPONSE ASSESSMENT").

Unlike in RECIST 1.1, each target lesion by RANO criteria has two perpendicular diameters collected. In order to calculate the target lesion response, the product of the two perpendicular diameters is calculated for each target lesion. Then the sum of the products of all target lesions is compared to the baseline or nadir to determine the target lesion response.

The non-target lesion response is collected on the field of "Non-target lesion present" in the Modified RANO Assessment page, and is evaluated based on both non-target lesion eCRF pages as shown above. However, no derivation will be performed from individual non-target lesion status to non-target lesion response.

The RANO response/progression criteria are summarized in [Table 4-3](#).

Please note that patients with non-measurable disease in brain at baseline are allowed to be enrolled in the study. According to RANO criteria, these patients with non-measurable disease in brain cannot have a response of CR or PR in the brain, and the best response they can achieve is stable disease (SD) in the brain.

**Table 4-3 Summary of the RANO response criteria**

	CR	PR	SD	PD
T1-Gd+ target lesions	None	≥50% decrease from baseline	<50% decrease from baseline but <25% increase from nadir	≥25% increase from nadir*
T1-Gd+ non-target lesions	Stable or improved	Stable or improved	Stable or improved	Increase*
T2/FLAIR	Stable or improved	Stable or improved	Stable or improved	Increase*
New Lesion	None	None	None	Present*
Corticosteroids	None	Stable or decrease	Stable or decrease	NA**
Clinical Status	Stable or improve	Stable or improve	Stable or improve	Deterioration*
Requirement for Response	All	All	All	Any*
CR=complete response; PR=partial response; SD=stable disease; PD=progressive disease *: Progression when this criterion is met **: Increase in corticosteroids alone will not be taken into account in determining progression in the absence of persistent clinical deterioration				

Two fields in the Modified RANO Assessment page will not be used for any data analysis in the study: “New enhancement outside radiation field?”, “Tumor present in histopathology”.

As in RECIST 1.1, PD should only be assigned if it is demonstrated by an objective assessment method as per RANO. Discontinuation due to disease progression or death due to progressive disease, without supporting objective evidence, will not be considered as PD.

As in RECIST 1.1, the same method of assessment and the same technique should be used to characterize each identified and reported lesion at baseline and during follow-up. The details of change in imaging modality are described in [Section 4.6.1](#).

The same principle will be followed for determining missing adequate tumor assessments, as described in [section 4.6.1](#).

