14.3.2 Response/progression categories

Complete response (CR)

All of the following criteria must be met:

- a. Complete disappearance of all enhancing measurable and non-measurable disease sustained for at least 4 weeks. In the absence of a confirming scan 4 weeks later, this scan will be considered only stable disease.
- b. No new lesions.
- c. All measurable and non-measurable lesions must be assessed using the same techniques as baseline.
- d. Participants must be on no steroids or on physiologic replacement doses only.
- e. Stable or improved non-enhancing (T2/FLAIR) lesions
- f. Stable or improved clinically, for clinical signs and symptoms present at baseline and recorded to be disease related

[figure not shown]
Participants with non-measurable disease cannot have a complete response. The best response possible is stable disease.

Partial response (PR)

All of the following criteria must be met:

- a. Greater than or equal to 50% decrease compared to baseline in the sum of products of perpendicular diameters of all measurable enhancing lesions sustained for at least 4 weeks. In the absence of a confirming scan 4 weeks later, this scan will be considered only stable disease.
- b. No progression of non-measurable disease.
- c. No new lesions.
- d. All measurable and non-measurable lesions must be assessed using the same techniques as baseline.
- e. The steroid dose at the time of the scan evaluation should be no greater than the dose at time of baseline scan.
- f. Stable or improved non-enhancing (T2/FLAIR) lesions on same or lower dose of corticosteroids compared to baseline scan.
- g. Stable or improved, for clinical signs and symptoms present at baseline and recorded to be disease related clinically.

Participants with non-measurable disease cannot have a partial response. The best response possible is stable disease.

Progressive disease (PD)

The following criterion must be met:

- a. 25% increase in sum of the products of perpendicular diameters of enhancing lesions (over best response or baseline if no decrease) on stable or increasing doses of corticosteroids **and/or one or more of the of the following:**
- b. Significant increase in T2/FLAIR non-enhancing lesion on stable or increasing doses of corticosteroids compared to baseline scan or best response following initiation of therapy, not due to co-morbid events (radiation therapy, demyelination, ischemic injury, infection, seizures, post-operative changes, or other treatment effects).

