- c. Any new lesion
- d. Clear clinical deterioration not attributable to other causes apart from the tumor (e.g. seizures, medication side effects, complications of therapy, cerebrovascular events, infection, etc.). The definition of clinical deterioration is left to the discretion of the investigator but it is recommended that a decline in the Karnofsky Performance Score (KPS) from 100 or 90 to 70 or less, a decline in KPS of at least 20 from 80 or less, or a decline in KPS from any baseline to 50 or less, for at least 7 days, be considered neurologic deterioration, unless attributable to co-morbid events or changes in corticosteroid dose.
- e. Failure to return for evaluation due to death or deteriorating condition.
- f. Clear progression of non-measurable disease

Stable disease (SD)

All of the following criteria must be met:

- a. Does not qualify for CR, PR, or progression.
- b. All measurable and non-measurable sites must be assessed using the same techniques as baseline.
- c. Stable non-enhancing (T2/FLAIR) lesions on same or lower dose of corticosteroids compared to baseline scan. In the event that the corticosteroid dose has been increased, the last scan considered to show stable disease will be the scan obtained when the corticosteroid dose was equivalent to the baseline dose.
- d. Stable clinically.

Unknown response status

Progressive disease has not been documented and one or more measurable or non-measurable lesions have not been assessed.

These RANO Response Criteria are also summarized in [Table 14-10](#):

[figure not shown]

Table 14-10 Summary of the RANO response criteria

	CR	PR	SD	PD#
T1-Gd +	None	≥50% decrease	<50% decrease but <25% increase	≥25% increase*
T2/FLAIR	Stable or decrease	Stable or decrease	Stable or decrease	Increase*
New Lesion	None	None	None	Present**
Corticosteroids	None	Stable or decrease	Stable or decrease	NA**
Clinical Status	Stable or improve	Stable or improve	Stable or improve	Deterioration*
Requirement for Response	All	All	All	Any*

CR=complete response; PR=partial response; SD=stable disease; PD=progressive disease
*: Progression when this criterion is met **: Increase in corticosteroids alone will not be taken into account in determining progression in the absence of persistent clinical deterioration

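### SAP 4.6.2 does not match protocol Appendix 3 on RANO complete response and progression, and SAP Table 3-1 does not record the differences

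*SAP*

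**What the plan says.** **Complete response.** Protocol 14.3.2 requires "Complete disappearance of all enhancing measurable and non-measurable disease sustained for at least 4 weeks". The protocol's summary, Table 14-10, has a single row for contrast-enhancing disease and enters *None* under CR. SAP Table 4-3 splits that row in two. For "T1-Gd+ non-target lesions" the CR cell reads *Stable or improved*. For PR, Appendix 3 asks only for "No progression of non-measurable disease".

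**Progression.** Appendix 3 lists clear clinical deterioration (d), "Failure to return for evaluation due to death or deteriorating condition" (e) and clear progression of non-measurable disease (f), each sufficient by itself. SAP Table 4-3 keeps "Deterioration" of clinical status as a stand-alone criterion and makes any *Increase* of enhancing non-target lesions PD. The text below the table then says "PD should only be assigned if it is demonstrated by an objective assessment method as per RANO" and "Discontinuation due to disease progression or death due to progressive disease, without supporting objective evidence, will not be considered as PD". On absent visits it adds "The same principle will be followed for determining missing adequate tumor assessments", pointing to SAP 4.6.1.

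**Use.** RANO OIRR, IDCR, TTIR and DOIR are exploratory. SAP 4.6.2 derives them from the overall lesion response collected on the eCRF, in the same way as under RECIST 1.1. Responses are additionally calculated from their components; Table 4-3 sets out the criteria. SAP Table 3-1, which lists changes to protocol analyses, covers time to response and PFS censoring only.

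**The concern.** SAP 4.6.2 refers the reader to Appendix 3 for further details and titles Table 4-3 a summary, so a programmer would expect the two to agree. They do not, and nothing says the differences are intended. A patient with persisting enhancing tumour in the brain can be labelled a calculated complete responder. A patient too ill to return, whom Appendix 3 counts as progressed, becomes a missing assessment. The treatment of clinical deterioration is also ambiguous: the table counts it, the sentence below asks for an objective method, and SAP 2.7.1 says that for RECIST clinical deterioration is not documented progression. At stake are the calculated CR/PR split, RANO DOIR and, on one reading, RANO IDCR.

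**Working it through.** The plan gives no figure to reproduce here, so the check compares rules.

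**Step 1. The rules side by side**

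| Item | Protocol Appendix 3 | SAP 4.6.2 |
|---|---|---|
| CR: enhancing non-target disease | Must disappear | *Stable or improved* is enough |
| PD: enhancing non-target disease | Clear progression | Any *Increase* |
| PD: clinical deterioration | Yes (d) | Yes in Table 4-3; in doubt from the text below it |
| PD: failure to return through death or deterioration | Yes (e) | No; handled as a missing assessment |

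**Step 2. Effect of Table 4-3 on a single assessment.** Take 4 target states (gone, at least 50% decrease, stable, at least 25% increase), 4 enhancing non-target states (gone, stable, minor increase, clear progression), 2 T2/FLAIR states, 2 new-lesion states, 3 steroid states (none, up to baseline, above baseline) and 2 clinical states. That gives 4 × 4 × 2 × 2 × 3 × 2 = 384 combinations. Each was classified once by the text of Appendix 3 and once by Table 4-3, with clinical deterioration and any T2/FLAIR increase counted as PD in both.

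- Same result: 357 + 6 + 6 + 4 + 1 = 374.
- Better under the SAP: 1. Targets gone, enhancing non-target lesions persisting and stable, everything else favourable, no steroids. This is PR by protocol and CR by the SAP.
- Worse under the SAP: 9. A minor increase of enhancing non-target lesions is PD by the SAP and not PD by protocol (4 are PR, 2 are SD, and 3 are SD or unclassifiable because steroids exceed baseline).

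374 + 1 + 9 = 384. These are counts of rule states, not patients, and the 9 assume that *Increase* includes an increase short of clear progression. The one upgraded state is a response under both rules, so OIRR, IDCR, TTIR and DOIR do not change.

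**Step 3. Failure to return, traced through the endpoints.** Under SAP 2.7.1, SD needs one assessment of SD or better more than 7 weeks after start of drug, and no confirming scan.

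- No valid post-baseline scan: PD by Appendix 3, unknown by the SAP. Neither is disease control.
- SD only at 7 weeks or earlier: not disease control under either rule.
- SD after week 7, then no return: best response SD under both.
- Unconfirmed PR after week 7, then no return: SD under both.
- Confirmed response, then no return: response under both.

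OIRR and IDCR therefore do not move. DOIR can. A living responder who stops returning because of deterioration is an event by Appendix 3; by SAP Table 2-2 the patient has no documented progression and is censored at the last adequate assessment. Death from any cause remains a DOIR event unless it follows two or more missing assessments, that is, more than D2 = (2 × 8) + 2 = 18 weeks after the last adequate one.

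**Step 4. If the objective-method sentence overrides the deterioration criterion.** Step 2 does not test this reading. A stable scan with clear clinical deterioration would no longer be PD. It becomes SD if clinical status is also set aside in the SD column, as under RECIST. If the SD column is kept as written, the visit fits no category. On the SD reading, a patient with this finding at the first assessment after week 7 moves from no control to control.

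**The case against.** The strongest reply is that Table 4-3 drives no planned endpoint. RANO endpoints come from the collected response, SAP Table 4-4 lists only investigator-reported and BIRC-reported sources, and all of this is exploratory. That stands, and it confines the CR cell and the *Increase* cell to the additional calculation. It does not dispose of the progression sentence or the missing-assessment rule, which are not worded as limited to that calculation.

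A second reply is that the sentence says *as per RANO* and sits under a table that keeps clinical deterioration, with clinical status a collected component, so deterioration recorded at an assessment still counts. That is a reasonable reading. But the sentence opens by likening RANO to RECIST 1.1, where SAP 2.7.1 excludes clinical deterioration, so the text does not settle the matter.

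A third is that protocol Table 14-10 also omits failure to return. True: the omission from Table 4-3 alone is no departure. The departure is in the text below it.

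A reader might infer that the SAP tilts RANO results favourably throughout. The documents do not support that: the CR cell changes no rate, and the *Increase* cell works the other way. A reader might also infer that each patient who dies or fails to return after SD shifts RANO IDCR. Step 3 shows otherwise.

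**Conclusion.** The mismatch is real, undisclosed and minor.

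- The CR cell contradicts Appendix 3 and turns a protocol PR into a calculated CR; only the calculated CR/PR split changes.
- The progression text loses criterion (e) and conflicts with the table's own deterioration criterion. Its one clear effect is on RANO DOIR, where a living responder who stops returning because of deterioration is censored instead of counted as an event. That lengthens the apparent duration.
- An effect on RANO IDCR arises only if the sentence overrides the deterioration criterion and the visit is then read as SD.
- The *Increase* cell is stricter than Appendix 3.

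No net direction can be stated, and no size in patients, because the documents do not say how many patients fall in these states. The primary, key secondary and modified RECIST intracranial endpoints are untouched.

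**What to change.** In SAP Table 4-3, set the CR cell for T1-Gd+ non-target lesions to *None*, and change the PD cell of that row to clear progression. For the RANO endpoints only, replace the objective-method text with Appendix 3 criteria (d) to (f). Give failure to return an event date, for example the next scheduled assessment as defined in protocol 14.2.25, and exempt it from the missing-assessment rule of SAP 4.6.1. State which recorded information identifies these patients, since the disposition reasons listed in protocol Appendix 2 have no entry for deterioration as such. Where a departure is intended, enter it in Table 3-1 with its rationale instead. It would also help to say what the calculated response is used for.

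The cost is two table cells, a few sentences and a small amount of extra programming for the event date and the exception. No new data collection is implied if the recorded reasons suffice.
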